Hypophysitis	Grade 2	Withhold	
 • Administer corticosteroids and initiate hormonal replacements as clinically indicated 	
 • Monitor for signs and symptoms of hypophysitis (including hypopituitarism and adrenal insufficiency)
	Grade 3 or 4	Withhold or permanently discontinue ^d		
Hyperthyroidism	Grade 2	Continue	
 • Treat with non-selective beta-blockers (eg, propranolol) or thionamides as appropriate 	
 • Monitor for signs and symptoms of thyroid disorders
	Grade 3 or 4	Withhold or permanently discontinue ^d		

General instructions:
 
 Severe and life-threatening irAEs should be treated with IV corticosteroids followed by oral steroids. Other immunosuppressive treatment should begin if the irAEs are not controlled by corticosteroids. Pembrolizumab must be permanently discontinued if the irAE does not resolve or the corticosteroid dose is not ≤ 10 mg/day within 12 weeks of the last pembrolizumab treatment. The corticosteroid taper should begin when the irAE is \leq Grade 1 and continue at least 4 weeks. If pembrolizumab has been withheld, pembrolizumab may resume after the irAE decreased to \leq Grade 1 after corticosteroid taper. 				
Hypothyroidism	Grade 2, 3, 4	Continue	
 Initiate thyroid replacement hormones (eg, levothyroxine or liothyronine) per standard of care 	
 Monitor for signs and symptoms of thyroid disorders
Nephritis: grading according to increased creatinine or acute kidney injury	Grade 2	Withhold	
 Administer corticosteroids (prednisone 1 – 2 mg/kg or equivalent) followed by taper 	
 Monitor changes of renal function
	Grade 3 or 4	Permanently discontinue		
Myocarditis	Grade 1 or 2	Withhold	
 Based on severity of AE administer corticosteroids 	
 Ensure adequate evaluation to confirm etiology and/or exclude other causes
	Grade 3 or 4	Permanently discontinue		
All Other immune-related AEs	Persistent Grade 2	Withhold	
 Based on severity of AE administer corticosteroids 	
 Ensure adequate evaluation to confirm etiology or exclude other causes
	Grade 3	Withhold or discontinue based on the event ^e		

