	Recurrent Grade 3 or Grade 4	Permanently discontinue		

^a AST/ALT: $>3.0 - 5.0 \times$ ULN if baseline normal; $>3.0 - 5.0 \times$ baseline, if baseline abnormal; bilirubin: $>1.5 - 3.0 \times$ ULN if baseline normal; $>1.5 - 3.0 \times$ baseline if baseline abnormal
 
^b AST/ALT: >5.0 to $20.0 \times$ ULN, if baseline normal; $>5.0 - 20.0 \times$ baseline, if baseline abnormal; bilirubin: $>3.0 - 10.0 \times$ ULN if baseline normal; $>3.0 - 10.0 \times$ baseline if baseline abnormal
 
^c AST/ALT: $>20.0 \times$ ULN, if baseline normal; $>20.0 \times$ baseline, if baseline abnormal; bilirubin: $>10.0 \times$ ULN if baseline normal; $>10.0 \times$ baseline if baseline abnormal
 
^d The decision to withhold or permanently discontinue pembrolizumab is at the discretion of the investigator or treating physician. If control achieved or \leq Grade 2, pembrolizumab may be resumed.
 
^e Events that require discontinuation include but are not limited to: Guillain-Barre Syndrome, encephalitis, Stevens-Johnson Syndrome and toxic epidermal necrolysis.
				

Patients who have a Grade 2 endocrinopathy, requiring ongoing hormonal replacement therapy, may restart pembrolizumab if treatment interruption was less than 12 weeks.

Dosing interruptions are permitted in the case of medical / surgical events or logistical reasons not related to study therapy (e.g., elective surgery, unrelated medical events, patient vacation, and/or holidays). Subjects should be placed back on study therapy within 3 weeks of the scheduled interruption, but no more than a maximum of 12 weeks for each instance. If the interruption is greater than 12 weeks the PI must discuss continuation in the trial with the Sponsor prior to administering additional therapy. For more info, please refer to Section [6.3](#).

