3.3 Endocrine

The following AE terms, if considered \geq Grade 3 or if \geq Grade 2 and require holding/discontinuation/ modification of pembrolizumab dosing, are considered ECIs and should be reported to the Sponsor within 24 hours of the event:

Adrenal insufficiency

Hyperthyroidism

Hypophysitis

Hypopituitarism

Hypothyroidism

Thyroid disorder

Thyroiditis

All attempts should be made to rule out other causes such as brain metastases, sepsis and/or infection. However the AE should be reported regardless of etiology.

Hypophysitis or other symptomatic endocrinopathy other than hypo- or hyperthyroidism

Grade 2-4 events:

Report as ECI if appropriate

Hold pembrolizumab

Rule out infection and sepsis with appropriate cultures and imaging.

Monitor thyroid function or other hormonal level tests and serum chemistries more frequently until returned to baseline values.

Pituitary gland imaging should be considered (MRIs with gadolinium and selective cuts of the pituitary can show enlargement or heterogeneity and confirm the diagnosis).

Treat with prednisone 40 mg p.o. or equivalent per day. When symptoms improve to Grade 1 or less, steroid taper should be started and continued over no less than 4 weeks. Replacement of appropriate hormones may be required as the steroid dose is tapered.

Permanently discontinue for inability to reduce corticosteroid dose to 10 mg or less of prednisone or equivalent per day within 12 weeks.

Hypophysitis with clinically significant adrenal insufficiency and hypotension, dehydration, and electrolyte abnormalities (such as hyponatremia and hyperkalemia) constitutes adrenal crisis.

Consultation with an endocrinologist may be considered.

Hyperthyroidism and Hypothyroidism

Thyroid disorders can occur at any time during treatment. Monitor patients for changes in thyroid function (at the start of treatment, periodically during treatment, and as indicated based on clinical evaluation) and for clinical signs and symptoms of thyroid disorders.

Grade 2 hyperthyroidism, Grade 2-4 hypothyroidism events:

Report as ECI if appropriate (see Table 1)

Monitor thyroid function or other hormonal level tests and serum chemistries more frequently until returned to baseline values.

Thyroid hormone and/or steroid replacement therapy to manage adrenal insufficiency.

Therapy with pembrolizumab can be continued while treatment for the thyroid disorder is instituted.

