3.7 Ocular

The following AE terms, if considered Grade ≥ 2 or requiring dose modification or use of systemic steroids to treat the AE, is considered an ECI and should be reported to the Sponsor within 24 hours of the event:

Uveitis

Iritis

All attempts should be made to rule out other causes such as metastatic disease, infection or other ocular disease (e.g. glaucoma or cataracts). However the AE should be reported regardless of etiology.

Course of Action

Grade 2 events:

Evaluation by an ophthalmologist is strongly recommended.

Treat with topical steroids such as 1% prednisolone acetate suspension and iridocyclitics.

Discontinue pembrolizumab as per protocol if symptoms persist despite treatment with topical immunosuppressive therapy.

Grade 3 events:

Evaluation by an ophthalmologist is strongly recommended

Hold pembrolizumab and consider permanent discontinuation as per specific protocol guidance.

Treat with systemic corticosteroids such as prednisone at a dose of 1 to 2 mg/kg per day. When symptoms improve to Grade 1 or less, steroid taper should be started and continued over no less than 4 weeks.

Permanently discontinue for inability to reduce corticosteroid dose to 10 mg or less of prednisone or equivalent per day within 12 weeks.

Grade 4 events:

Evaluation by an ophthalmologist is strongly recommended

Permanently discontinue pembrolizumab.

Treat with corticosteroids as per Grade 3 above

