3.9 Skin

Rash and Pruritus

The following AEs should be considered as ECIs, if \geq Grade 3 and should be reported to the Sponsor within 24 hours of the event:

Pruritus

Rash

Rash generalized

Rash maculo-papular

In addition to CTCAE Grade 3 rash, any rash that is considered clinically significant, in the physician's judgment, should be treated as an ECI. Clinical significance is left to the physician to determine, and could possibly include rashes such as the following:

rash with a duration >2 weeks; OR

rash that is >10% body surface area; OR

rash that causes significant discomfort not relieved by topical medication or temporary cessation of study drug.

Other Skin ECIs

The following AEs should always be reported as ECIs, regardless of grade, and should be reported to the Sponsor within 24 hours of the event:

Dermatitis exfoliative

Erythema multiforme

Steven's Johnson syndrome

Toxic epidermal necrolysis

Please note, the AE should be reported regardless of etiology.

Course of Action

Grade 2 events:

Symptomatic treatment should be given such as topical glucocorticosteroids (e.g., betamethasone 0.1% cream or hydrocortisone 1%) or urea-containing creams in combination with oral anti-pruritics (e.g., diphenhydramine HCl or hydroxyzine HCl).

Treatment with oral steroids is at physician's discretion for Grade 2 events.

Grade 3 events:

Hold pembrolizumab.

Consider Dermatology Consultation and biopsy for confirmation of diagnosis.

Treatment with oral steroids is recommended, starting with 1 mg/kg prednisone or equivalent once per day or dexamethasone 4 mg four times orally daily. When symptoms improve to Grade 1 or less, steroid taper should be started and continued over no less than 4 weeks.

Permanently discontinue for inability to reduce corticosteroid dose to 10 mg or less of prednisone or equivalent per day within 12 weeks.

Grade 4 events:

Permanently discontinue pembrolizumab.

Dermatology consultation and consideration of biopsy and clinical dermatology photograph.

Initiate steroids at 1 to 2 mg/kg prednisone or equivalent. When symptoms improve to Grade 1 or less, steroid taper should be started and continued over no less than 4 weeks.

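### For Grade 3 Stevens-Johnson syndrome and Grade 3 encephalitis, Appendix G requires discontinuation while Appendix I says hold; the two appendices need to be reconciled

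*Combined protocol and SAP*

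**What the plan says.** **Appendix G, Table 1.** The table has no row for skin, neurologic or ocular events, so these fall under All Other immune-related AEs. The row has three levels:

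- "Persistent Grade 2": withhold.
- Grade 3: "Withhold or discontinue based on the event", with footnote e.
- "Recurrent Grade 3 or Grade 4": permanently discontinue.

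Footnote e reads: "Events that require discontinuation include but are not limited to: Guillain-Barre Syndrome, encephalitis, Stevens-Johnson Syndrome and toxic epidermal necrolysis".

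**Appendix I, section 3.9 (Skin).** Toxic epidermal necrolysis and "Steven's Johnson syndrome" are listed under Other Skin ECIs, reportable at any grade. A single course of action follows for the whole section, rash and pruritus included. At Grade 3 it is to hold pembrolizumab, and the only route to a permanent stop is: "Permanently discontinue for inability to reduce corticosteroid dose to 10 mg or less of prednisone or equivalent per day within 12 weeks". At Grade 4 pembrolizumab is permanently discontinued.

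**Appendix I, section 1 (Overview).** Discontinuing is defined as permanent. Holding is defined as stopping with resumption possible if the patient meets the criteria for it. The same section refers dose-modification questions to the specific language of the protocol.

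**Sections 5.6 and 5.7.** Both point to Appendices G and H for toxicity management. Section 5.6 also makes discontinuation of study treatment irreversible.

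**The concern.** An investigator with a Grade 3 case of Stevens-Johnson syndrome finds two instructions in one protocol. Appendix G says the event requires discontinuation. The dedicated skin section of Appendix I says hold, makes no exception for this event, and gives a different test for permanent stopping.

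The consequence is for the individual patient. Under one text, a participant could be considered for further infusions after a reaction that the other text lists as requiring discontinuation. Under the other, a participant permanently loses the remaining infusions. Because treatment is blinded, investigators apply these rules in both arms. The issue concerns safety and uniform conduct across sites. It does not touch the sample size, the error control or the intention-to-treat analysis.

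**Working it through.** No calculation applies. The check compares the events in footnote e, and two others that might fall in the same row, grade by grade, using Appendix I's own definitions of hold and discontinue.

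| Event and grade | Appendix G | Appendix I | Result |
|---|---|---|---|
| Stevens-Johnson syndrome, Grade 3 | Discontinuation required (footnote e) | 3.9: hold; permanent stop only if steroid reduction fails | Conflict |
| Toxic epidermal necrolysis, Grade 3 | Discontinuation required (footnote e) | 3.9: as above | Conflict, if Grade 3 exists for this term |
| Either skin event, Grade 4 | Permanently discontinue | 3.9: permanently discontinue | Agree |
| Encephalitis, Grade 3 | Discontinuation required (footnote e) | Not named; 3.10 catch-all: hold, restart possible if steroids are reduced | Conflict |
| Encephalitis, Grade 4 | Permanently discontinue | 3.10: discontinue | Agree |
| Guillain-Barré syndrome, Grades 3 and 4 | Discontinue | 3.6: discontinue | Agree |
| Uveitis or iritis, persistent Grade 2 | Withhold | 3.7: see below | Ambiguous |
| Adrenal insufficiency, Grade 4 | Depends on the row | 3.3: hold | Ambiguous |

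**Skin events.** Section 3.9 does not itself mention restarting. That possibility comes from the definition of a hold in section 1 of Appendix I and depends on resumption criteria being met. Even so, *must stop* and *hold unless steroids cannot be reduced* are different instructions for the same event and grade.

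**Toxic epidermal necrolysis.** Whether it can be Grade 3 depends on CTCAE v4.03, which Appendix D only links to. The Stevens-Johnson mismatch does not depend on this point.

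**Encephalitis.** Appendix I does not name it. If the physician considers a Grade 3 case immune-related, it falls under section 3.10, which holds treatment and expressly allows a restart if steroids can be reduced in time.

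**Uveitis and iritis.** Section 3.7 says: "Discontinue pembrolizumab as per protocol if symptoms persist despite treatment with topical immunosuppressive therapy". The reference to the protocol can be read as sending the reader back to Appendix G, which withholds. The triggers also differ: failure of topical therapy in one, persistence at Grade 2 in the other.

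**Adrenal insufficiency.** Section 3.3 holds for Grades 2 to 4 under the heading "Hypophysitis or other symptomatic endocrinopathy other than hypo- or hyperthyroidism". In Appendix G the term has no row of its own, but the hypophysitis row names it in the monitoring column. That row's Grade 3 or 4 action is to withhold or permanently discontinue at the physician's discretion, which is compatible with a hold. Only if the event is placed in the All Other row do the texts diverge.

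**Which text governs.** Sections 5.6 and 5.7 send the site to Appendices G and H. Appendix H has no skin, ocular or neurologic section and refers the site to the ECI guidance document, which is Appendix I, for greater detail. Appendix I then sends dose-modification questions back to the protocol, of which it is itself a part. No sentence in this loop says that Appendix G overrides Appendix I.

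**The case against.** The strongest reply is that the documents already indicate an order of precedence. Appendix I is a programme-wide guidance document. It says that its recommendations are guidelines and that the protocol's specific language should be followed on dose modification. The trial's own stopping section points to Appendices G and H, not I. The skin section has no resumption criteria, so a site looking for them would come to Appendix G and meet footnote e there. In section 3.10, the sentence allowing a restart also refers to the protocol, at least for dose modification.

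Most of this stands, and it lowers the practical risk. It does not remove the contradiction. Appendix I is bound into the protocol and says that it gives specific direction on when to hold and when to discontinue. Appendix H sends sites there for detail. The Grade 3 skin instruction carries no reference back to the protocol.

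A reader might also infer that the whole All Other row is contradicted, with opposite actions for persistent Grade 2 uveitis or iritis and for Grade 4 adrenal insufficiency. The documents do not support that. The first rule defers to the protocol, and the second event may belong to the hypophysitis row. Both are unclear wording, not established opposites.

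**Conclusion.** The point holds as a narrow internal contradiction. It covers Grade 3 Stevens-Johnson syndrome and Grade 3 encephalitis, and Grade 3 toxic epidermal necrolysis on the assumption that CTCAE v4.03 allows that grade. For encephalitis it also assumes that the physician considers the event immune-related, which brings it under section 3.10. Both appendices discontinue at Grade 4, and they agree on Guillain-Barré syndrome at Grades 3 and 4.

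Its size cannot be put in patients. The documents give no incidence for these events, and any count would rest on an invented rate. A reader might also infer that sites will re-expose patients after these reactions. The text shows only that one of two instructions leaves this open, subject to resumption criteria.

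I rate it as something that should be fixed before the appendices are next issued, not as a fault that undermines the trial. This review takes no position on which action is clinically right.

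**What to change.** Reconcile the All Other row and footnote e of Appendix G with Appendix I sections 3.9 and 3.10, so that each event named in the footnote has one action at each grade in both places. In section 3.9 this may mean separating the course of action for Other Skin ECIs from that for rash and pruritus. Encephalitis should be named in Appendix I or explicitly carved out of the catch-all.

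At the same time, clarify what the reference to the protocol means in section 3.7, and which Appendix G row covers adrenal insufficiency for the purposes of section 3.3. State in both appendices which one governs if they differ. The sponsor's safety physicians decide which action stands.

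The cost is a wording change to two appendices and a notice to sites. No procedure, visit or analysis changes.

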Appendix H: Supportive care

Subjects should receive appropriate supportive care measures as deemed necessary by the treating investigator. Suggested supportive care measures for the management of adverse events with potential immunologic etiology are outlined below and in greater detail in the ECI guidance document. Where appropriate, these guidelines include the use of oral or intravenous treatment with corticosteroids as well as additional anti-inflammatory agents if symptoms do not improve with administration of corticosteroids. Note that several courses of steroid tapering may be necessary as symptoms may worsen when the steroid dose is decreased. For each disorder, attempts should be made to rule out other causes such as metastatic disease or bacterial or viral infection, which might require additional supportive care. The treatment guidelines are intended to be applied when the investigator determines the events to be related to pembrolizumab.

Note: if after the evaluation the event is determined not to be related, the investigator is instructed to follow the ECI reporting guidance but does not need to follow the treatment guidance (as outlined in the ECI guidance document). Refer to Section 5.2.1 for infusion modification.

It may be necessary to perform conditional procedures such as bronchoscopy, endoscopy, or skin photography as part of evaluation of the event. Suggested conditional procedures, as appropriate, can be found in the ECI guidance document.

◆ **Pneumonitis:**

- ◆ For **Grade 2 events**, treat with systemic corticosteroids. When symptoms improve to Grade 1 or less, steroid taper should be started and continued over no less than 4 weeks.
- ◆ For **Grade 3-4 events**, immediately treat with intravenous steroids. Administer additional anti-inflammatory measures, as needed.
- ◆ Add prophylactic antibiotics for opportunistic infections in the case of prolonged steroid administration.

◆ **Diarrhea/Colitis:**

Subjects should be carefully monitored for signs and symptoms of enterocolitis (such as diarrhea, abdominal pain, blood or mucus in stool, with or without fever) and of bowel perforation (such as peritoneal signs and ileus).

- ◆ All subjects who experience diarrhea/colitis should be advised to drink liberal quantities of clear fluids. If sufficient oral fluid intake is not feasible, fluid and electrolytes should be substituted via IV infusion. For Grade 2 or higher diarrhea, consider GI consultation and endoscopy to confirm or rule out colitis.
- ◆ For **Grade 2 diarrhea/colitis** that persists greater than 3 days, administer oral corticosteroids.
- ◆ For **Grade 3 or 4 diarrhea/colitis** that persists > 1 week, treat with intravenous steroids followed by high dose oral steroids.

- ◆ When symptoms improve to Grade 1 or less, steroid taper should be started and continued over no less than 4 weeks.
- ◆ **Type 1 diabetes mellitus (if new onset, including diabetic ketoacidosis [DKA]) or \geq Grade 3 Hyperglycemia, if associated with ketosis (ketonuria) or metabolic acidosis (DKA)**
 - ◆ For **T1DM** or **Grade 3-4** Hyperglycemia
 - ◆ Insulin replacement therapy is recommended for Type I diabetes mellitus and for Grade 3-4 hyperglycemia associated with metabolic acidosis or ketonuria.
 - ◆ Evaluate patients with serum glucose and a metabolic panel, urine ketones, glycosylated hemoglobin, and C-peptide.
- ◆ **Hypophysitis:**
 - ◆ For **Grade 2** events, treat with corticosteroids. When symptoms improve to Grade 1 or less, steroid taper should be started and continued over no less than 4 weeks. Replacement of appropriate hormones may be required as the steroid dose is tapered.
 - ◆ For **Grade 3-4** events, treat with an initial dose of IV corticosteroids followed by oral corticosteroids. When symptoms improve to Grade 1 or less, steroid taper should be started and continued over no less than 4 weeks. Replacement of appropriate hormones may be required as the steroid dose is tapered.
- ◆ **Hyperthyroidism or Hypothyroidism:**

Thyroid disorders can occur at any time during treatment. Monitor patients for changes in thyroid function (at the start of treatment, periodically during treatment, and as indicated based on clinical evaluation) and for clinical signs and symptoms of thyroid disorders.

- ◆ **Grade 2** hyperthyroidism events (and **Grade 2-4** hypothyroidism):
 - ◆ In hyperthyroidism, non-selective beta-blockers (e.g. propranolol) are suggested as initial therapy.
 - ◆ In hypothyroidism, thyroid hormone replacement therapy, with levothyroxine or liothyronine, is indicated per standard of care.
- ◆ **Grade 3-4** hyperthyroidism
 - ◆ Treat with an initial dose of IV corticosteroid followed by oral corticosteroids. When symptoms improve to Grade 1 or less, steroid taper should be started and continued over no less than 4 weeks. Replacement of appropriate hormones may be required as the steroid dose is tapered.
- ◆ **Hepatic:**
 - ◆ For **Grade 2** events, monitor liver function tests more frequently until returned to baseline values (consider weekly).
 - ◆ Treat with IV or oral corticosteroids
 - ◆ For **Grade 3-4** events, treat with intravenous corticosteroids for 24 to 48 hours.

- ◆ When symptoms improve to Grade 1 or less, a steroid taper should be started and continued over no less than 4 weeks.
- ◆ **Renal Failure or Nephritis:**
 - ◆ For **Grade 2** events, treat with corticosteroids.
 - ◆ For **Grade 3-4** events, treat with systemic corticosteroids.
 - ◆ When symptoms improve to Grade 1 or less, steroid taper should be started and continued over no less than 4 weeks.
- ◆ **Management of Infusion Reactions:** Signs and symptoms usually develop during or shortly after drug infusion and generally resolve completely within 24 hours of completion of infusion.

Table 1 below shows treatment guidelines for subjects who experience an infusion reaction associated with administration of pembrolizumab (MK-3475).

Dose Modification and Toxicity Management of Infusion Reactions Related to Pembrolizumab

Table 1 Infusion Reaction Treatment Guidelines

NCI CTCAE Grade	Treatment	Premedication at subsequent dosing
Grade 1 Mild reaction; infusion interruption not indicated; intervention not indicated	Increase monitoring of vital signs as medically indicated until the subject is deemed medically stable in the opinion of the investigator.	None
Grade 2 Requires therapy or infusion interruption but responds promptly to symptomatic treatment (e.g., antihistamines, NSAIDS, narcotics, IV fluids); prophylactic medications indicated for <=24 hrs	
Stop Infusion
 
Additional appropriate medical therapy may include but is not limited to:
 
IV fluids Antihistamines NSAIDS Acetaminophen Narcotics
 
Increase monitoring of vital signs as medically indicated until the participant is deemed medically stable in the opinion of the investigator.
 
If symptoms resolve within one hour of stopping drug infusion, the infusion may be restarted at 50% of the original infusion rate (e.g., from 100 mL/hr to 50 mL/hr). Otherwise dosing will be held until symptoms resolve and the participant should be premedicated for the next scheduled dose.
 
Participants who develop Grade 2 toxicity despite adequate premedication should be permanently discontinued from further trial treatment administration.
	
Subject may be premedicated 1.5h (± 30 minutes) prior to infusion of study intervention with:
 
Diphenhydramine 50 mg po (or equivalent dose of antihistamine).
 
Acetaminophen 500-1000 mg po (or equivalent dose of analgesic).

NCI CTCAE Grade	Treatment	Premedication at subsequent dosing
Grades 3 or 4 Grade 3: Prolonged (i.e., not rapidly responsive to symptomatic medication and/or brief interruption of infusion); recurrence of symptoms following initial improvement; hospitalization indicated for other clinical sequelae (e.g., renal impairment, pulmonary infiltrates) Grade 4: Life-threatening; pressor or ventilatory support indicated	Stop Infusion. Additional appropriate medical therapy may include but is not limited to: IV fluids Antihistamines NSAIDS Acetaminophen Narcotics Oxygen Pressors Corticosteroids Epinephrine** Increase monitoring of vital signs as medically indicated until the subject is deemed medically stable in the opinion of the investigator. Hospitalization may be indicated. **In cases of anaphylaxis, epinephrine should be used immediately. Participant is permanently discontinued from further study drug intervention.	No subsequent dosing

Appropriate resuscitation equipment should be available in the room and a physician readily available during the period of drug administration.
 
For further information, please refer to the Common Terminology Criteria for Adverse Events v4.03 (CTCAE) at http://ctep.cancer.gov
		

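### Appendix H ties IV steroids for Grade 3 or 4 diarrhea/colitis to more than a week of symptoms; Appendices G and I set no wait at those grades

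*Combined protocol and SAP*

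**What the plan says.** Section 5.7 sends sites to Appendices G and H for the management of toxicity and for supportive care, and does not rank them.

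- **Appendix H, Diarrhea/Colitis.** At Grade 2, the instruction is for an event "that persists greater than 3 days, administer oral corticosteroids". At Grade 3 or 4, it is for an event "that persists > 1 week, treat with intravenous steroids followed by high dose oral steroids". Nothing else in the block starts steroids at Grade 3 or 4.
- **Appendix H, introduction.** The measures are described as suggested, care is left to the treating investigator, and the measures are said to be "outlined below and in greater detail in the ECI guidance document". That guidance document is Appendix I.
- **Appendix G.** General instruction 1 gives IV followed by oral corticosteroids for severe and life-threatening immune-related events. The diarrhea/colitis row of its Table 1 gives 1 to 2 mg/kg prednisone or equivalent, then a taper. Neither has a duration condition, and the introduction stresses starting treatment early.
- **Appendix I, section 3.2.** Grade 3 receives IV methylprednisolone 125 mg followed by high-dose oral steroids, and Grade 4 is managed as Grade 3. Neither has a wait. Its duration conditions concern Grade 2.

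**The concern.** Read literally, Appendix H starts oral steroids in a Grade 2 patient after 3 days but has no steroid trigger in the first week of a severe or life-threatening event. The routes differ (oral at Grade 2, IV at Grade 3 or 4), but H has no other steroid line at the higher grades to fill that week. Appendices G and I, read alone, would have such a patient on steroids without any stated wait.

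What is at stake is patient safety. The Appendix H block itself warns of bowel perforation, and Section 3.3.1 requires patients to have no evidence of disease at entry, so avoidable toxicity carries particular weight. No effect on endpoints, power or any analysis is claimed.

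**Working it through.** No formula applies; the check compares the texts.

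**Step 1: the steroid trigger in each appendix**

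| Source | Grade 2 | Grade 3 | Grade 4 |
|---|---|---|---|
| Appendix G (instruction 1; Table 1, colitis row) | steroids, no duration stated | steroids, no duration stated | steroids, no duration stated |
| Appendix H | oral after > 3 days | IV after > 1 week | IV after > 1 week |
| Appendix I, 3.2 | oral after > 3 days, or with blood or mucus; moves to the Grade 3 course on worsening or after > 3 days in one line, after > 1 week in another | IV, no duration stated | as Grade 3 |

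At Grades 3 and 4, H stands alone.

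**Step 2: the other Grade 3-4 lines in Appendix H.** The count covers organ-specific lines that give corticosteroids. Infusion reactions are left out, and the type 1 diabetes line is left out because it gives insulin.

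1. Pneumonitis: "immediately treat with intravenous steroids. Administer additional anti-inflammatory measures, as needed". No wait.
2. Diarrhea/colitis: persistence beyond 1 week.
3. Hypophysitis: "treat with an initial dose of IV corticosteroids followed by oral corticosteroids". No wait.
4. Hyperthyroidism: "Treat with an initial dose of IV corticosteroid followed by oral corticosteroids". No wait.
5. Hepatic: "treat with intravenous corticosteroids for 24 to 48 hours". No wait.
6. Renal failure or nephritis: "events, treat with systemic corticosteroids". No wait; the route is not restricted to IV.

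One of six has a persistence condition and five of six have none. H gives no reason for the exception.

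**Step 3: where one week appears elsewhere.** The Grade 3 heading in Appendix I, 3.2 brings in Grade 2 diarrhea lasting more than a week, so there the duration qualifies Grade 2. Comparing IV with IV, Appendix I's longest wait at Grade 2 is > 7 days and H's wait at Grade 3 or 4 is also > 7 days (7 - 7 = 0 days apart). H thus waits as long for severe colitis as Appendix I ever does for moderate diarrhea. This pattern suggests that the condition was attached to the wrong grade.

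**Step 4: the practical gap.** Under Appendix I, if IV then oral steroids have not reduced symptoms within 48 to 72 hours, additional anti-inflammatory measures are considered. Since 72 / 24 = 3 days, a patient managed under I from onset could reach that step by about day 3, before H's first IV trigger (> 7 days) is met.

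**Step 5: does any text settle which appendix governs?** Section 5.7 cites G and H without ranking, and Section 5.6 also cites both. Section 7.2.3 refers to Appendix I for Events of Clinical Interest. The Overview of Appendix I defers to protocol language on treatment options, which can send a reader back to H or equally to G. No rule of precedence results.

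**The case against.** The conflict itself is not disputed; the objection concerns its weight.

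- **H is advisory.** It does not say that steroids are given only after a week, it leaves care to the investigator, and it points to Appendix I. The Overview of Appendix I likewise calls for individual clinical judgment. This stands and lowers the likelihood of harm. But a pointer to more detail does not say which text prevails, and here Appendix I differs from H rather than expanding on it.
- **Other safeguards exist.** Colitis and diarrhea of Grade 2 or higher are Events of Clinical Interest (Section 16.1) and must be reported within 24 hours (Section 16.6). H also calls for monitoring for perforation, fluids, and consideration of endoscopy from Grade 2. These stand too, but none of them starts steroids.
- **Exposure may be over.** Accrual of 52 months from January 2016 (Section 8.1.1) would end around spring 2020, and about a year of treatment takes most infusions to around mid-2021. The version date is not visible in the text reviewed, so this cannot be settled. Appendix G notes that immune-related events may appear months after the last dose.
- **The fix does not harmonise everything.** At Grade 2, G states no wait while H and I wait > 3 days, and Appendix I gives two different times for escalation. This is true, but those are separate points about a less severe grade and are no reason to leave the Grade 3-4 line as it is.
- **The 1-of-6 count mixes routes**, because the renal line is not limited to IV. This is correct, but the count concerns the persistence condition, not the route.

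**Conclusion.** The line in Appendix H is wrong as written. At Grades 3 and 4 it sets a trigger of more than 7 days where Appendices G and I state none, and it is the exception among H's own six Grade 3-4 corticosteroid lines. The mitigating text reduces the chance of harm but does not tell a site which instruction to follow, and guidance should not depend on clinicians overriding it.

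The conclusion rests on reading the persistence clause as the condition for giving IV steroids, which is its plain sense since H has no other steroid instruction for these grades. That it arose as an editing slip is an inference, and the finding does not depend on it. The number of patients affected cannot be derived from the documents. It should be fixed as a patient-safety wording error; the statistical design is untouched.

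**What to change.** In Appendix H, remove the persistence condition from the Grade 3 or 4 diarrhea/colitis line, so that it directs IV steroids followed by high-dose oral steroids without a waiting period, and notify sites. H then agrees with G and I at these grades; its Grade 2 line and the investigator's discretion are unchanged. The cost is one deleted phrase and a site notification, with no change to sample size, endpoints or analyses.
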